4.1 Patient Inclusion Criteria

- Acute myeloid leukemia according to the WHO classification
- Informed consent in place for a registry study and/or a randomized study of the Study Alliance Leukemia (SAL) including the Heidelberg Leukemia Network (HeLeNe) covering assessment of MRD by MPFC in the reference laboratories in Heidelberg and Dresden.

4.2 Patient Exclusion Criteria

- No signed informed consent compliant with the requirements of PERDAM

4.3 Withdrawal of Patients

A patient must be withdrawn from the study for the following reasons:

- At any time at their own request.
- Withdrawal of patient's consent to use their data

If the patient withdraws consent for disclosure of information, no additional data can be collected. Data already being transferred to the PERDAM database before the withdrawal may still be used unless the signed Informed Consent of the respective clinical trials imposes a deletion.

4.4 Premature Closure of the study and exclusion of participating studies

The trial can be prematurely closed or suspended by the PI. Participating studies can be excluded. Furthermore, the IEC themselves may decide to stop or suspend the study.

Reasons for premature closure or exclusion of participating studies:

- Non-compliance with the protocol
- Poor data quality
- No recruitment in 6 months
- Non-adequate IC

The PIs of all participating and affected studies have to be informed immediately about a cessation/suspension of the study. No further data will be collected.

5 Sample procurement & shipment

5.1 Sample shipment to the University Hospital Heidelberg

Send biosamples and their accompanying routing forms at room temperature, Monday to Friday, carrier for next day delivery before 9 a.m., to

Universitätsklinikum Heidelberg
Medizinische Klinik, [name] ,
Weiterleitung an die **Hämatologische Diagnostik**/Leitung PD. [name].
[name],
[name]
[contact] (Frau [name])

e-mail: [contact]
[contact]

5.2 ***Sample shipment to the University Hospital Dresden***

Send biosamples and their accompanying routing forms at room temperature, Monday to Friday, via overnight carrier for next day, delivery before 9 a.m., to:

Hämatologisches Labor [name]
Medizinische Klinik und Poliklinik I
Universitätsklinikum Carl Gustav Carus
[name]
[name]
Germany
[contact]
Email: [contact]

6 **MRD assessment by MPFC**

6.1 ***Sample preparation and measurement***

In order to obtain comparable results, instrument set up, sample preparation and surface staining will be performed in the same manner in both laboratories. The procedures are based on the HAROMIZE initiative [34] and listed in detail in the lab manual.

6.2 ***Regular MRD assessment conferences and cross validation***

In terms of cross validation and harmonization the same SOPs for MRD assessment by MPFC are used in the two laboratories. In addition, regular MRD assessment phone/web conferences are held every three months to discuss all cases of the three month time period and achieve agreement. A cross validation between the two laboratories is performed at the beginning and thereafter every 6 months during the PERDAM study conduct with divided samples sent out to the two laboratories and measured in both laboratories at the same time-points, at diagnosis/relapse and after induction/salvage therapy (see lab manual).

7 **Perdam Database**

Data management is performed by the NCT trial center. The Web-based registration platform for the PERDAM study is based on the generic data protection concept of the Telematics Platform for Medical Research Networks (Telematikplattform für Medizinische Forschungsnetze, TMF) using appropriate measures for data protection and disaster recovery.

7.1 ***Registration process and data input***

During the registration process every patient already identified via a unique pseudonym consisting of short name of the randomized study and the study-specific patient-identifier receives a second unique second pseudonym, the PERDAM identifier. Data obtained in the two laboratories are handled in certified lab-specific IT-systems and transferred to the PERDAM databases via secured file-upload or are manually documented. The PERDAM database fulfills EudraLex Volume 4 Annex 11 and FDA Title 21 CFR Part 11 requirements. MRD assessed by MPFC is documented for patients who at least have one MPFC result at diagnosis/relapse describing the LAPs for an individual patient and one MRD assessment by MPFC after induction/salvage therapy. Patients responding to induction/salvage therapy but without

evaluable LAPs are documented with the different to normal approach in the PERDAM database. In addition, the MRD assessment after completion of consolidation therapy is included as third assessment time point. The registration process, file-upload and manual input are described in detail in the PERDAM database manual (separates document).

8 Clinical data

The demographic, laboratory, clinical and outcome data of the interventional randomized clinical trials are documented in trial-specific case report forms and after validation stored in trial-specific databases (Trial-databases) fulfilling EudraLex Volume 4 Annex 11 and FDA Title 21 CFR Part 11. Linkage between data of the Trial-databases and the PERDAM database are achieved via the uniform patient-specific pseudonym. Regular data exports from the Trial-databases including a core dataset (excluding explicitly the randomization) including data assessed at diagnosis/relapse (age at diagnosis/relapse, sex, date of diagnosis/relapse, WBC, bone marrow blast percentage, AML-entity according to WHO-2016), induction/salvage treatment (start of induction/salvage treatment, dose-reduction (yes/no) of induction- and/or consolidation therapy, response to induction/salvage treatment, date of assessment, date of response), consolidation treatment data (start of consolidation treatment, date of allogeneic HCT) and outcome data (date of relapse, date of last follow-up or date of death, vital status) are implemented on a three monthly basis. These data are imported into the PERDAM database to provide clinical background for the regular MRD-assessment conferences.

9 Statistical analyses

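### Section 8 gives the MRD conferences relapse and death data, and the protocol neither masks members to outcome nor says whether the laboratory or the agreed MRD value is analysed

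*Combined protocol and SAP*

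**What the plan says.** Section 8 describes a core dataset sent from the trial databases to the PERDAM database: "Regular data exports from the Trial-databases including a core dataset (excluding explicitly the randomization"). Besides baseline data, response, the start of consolidation and any transplant date, it carries the endpoints: "outcome data (date of relapse, date of last follow-up or date of death, vital status) are implemented on a three monthly basis". The purpose follows directly: "These data are imported into the PERDAM database to provide clinical background for the regular MRD-assessment conferences".

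Section 6.2 describes the conferences: "regular MRD assessment phone/web conferences are held every three months to discuss all cases of the three month time period and achieve agreement". Section 3.1.2 adds that the regular meetings work from data already in the database and serve to harmonise MRD evaluations as well as laboratory procedures. Section 10 counts the conferences among the measures that assure the quality of laboratory analyses.

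Section 9.1.1 times the first MRD assessment with the morphological remission assessment after induction or salvage, and uses it for the primary hypothesis. Section 9.1.2 makes OS the primary survival endpoint.

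Two manuals are cited but not included: laboratory procedures are "listed in detail in the lab manual" (section 6.1), and registration, "file-upload and manual input are described in detail in the PERDAM database manual" (section 7.1). Section 9.1.4 defers a detailed SAP until before database closure.

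**The concern.** MRD after induction or salvage is the variable whose value as a surrogate for OS is being tested. Under section 8 the people who discuss it, and seek agreement on it, have relapse, death and vital status in front of them. If a reading were settled with that knowledge, part of its association with survival would have been put there by the readers.

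There is room for judgement. Section 1.2 describes the different-from-normal method as a visual comparison with normal or regenerating marrow. Responders without "evaluable LAPs are documented with the different to normal approach in the PERDAM database" (section 7.1), and section 3.1.2 lets a whole study use that method.

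At stake is mainly credibility. The study wants confirmatory, prospective evidence that MRD could support earlier drug approval. A critic could call a positive result circular, and the authors could answer only if a value untouched by outcome knowledge had been kept and designated for analysis.

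**Working it through.** **Step 1. Do the stated protections hide outcome?**

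- Leaving randomisation out of the export (section 8) hides the arm, not relapse or death.
- Pseudonymised samples (synopsis) hide identity.
- Certified laboratory systems and a database meeting Annex 11 and Part 11 (section 7.1) concern how data are held. That section does not say who sees outcome or which value is analysed.
- The timing rule in section 9.1.1 fixes the time point, not the choice between laboratory and agreed reading.
- The meetings' use of documented data (section 3.1.2) implies that a value exists beforehand. No text fixes that value before outcome is linked or discussed.

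So neither outcome masking nor the choice of reading is covered in the protocol.

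**Step 2. How large could the effect be?** The plan gives no figure on this point, and its power statement does not enter, so every input below except R_T is assumed.

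Inputs: 40% MRD positive in the control arm; MRD-OS hazard ratio 2.0; log odds ratios across trials with mean 0 and SD 0.4; exponential OS within each MRD group, control median 24 months (range tried 18 to 48); uniform censoring over 12 to 60 months; deaths only; no sampling error. From section 9.1.3: R_T of 0.8 (null boundary) and 0.9 (planning value).

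Revision rules, applied blind to arm with probability q of 0.1 or 0.2:

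- Two-way: negatives who have died become positive, and positives still alive become negative.
- Upgrade-only: only the first of these moves.

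Revised positive share in an arm (two-way) = p + (1−p)·D·q − p·A·q. D is the probability that a negative patient has died by the conference, and A the probability that a positive patient is alive.

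Control-arm example, 3 months known, q = 0.2:

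- The hazard h in negatives solves 0.6·exp(−24h) + 0.4·exp(−48h) = 0.5, so h = 0.0215.
- D = 1 − exp(−3h) = 0.063 and A = exp(−6h) = 0.879.
- Share = 0.4 + 0.6·0.063·0.2 − 0.4·0.879·0.2 = 0.4 + 0.0075 − 0.0703 = 0.337.

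About 7.8% of calls move, and 0.0703/0.0778 = 90% of those are positives who are simply still alive. Upgrade-only moves 0.75%.

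R_T shift is the correlation of the revised log OR with the Cox log HR, minus the same correlation before revision (median 24 months):

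| True R_T | Outcome known | Two-way, q 0.1 / 0.2 | Upgrade-only, q 0.1 / 0.2 |
|---|---|---|---|
| 0.8 | 1.5 months | +0.0009 / +0.0021 | +0.0007 / +0.0013 |
| 0.8 | 3 months | +0.0024 / +0.0054 | +0.0013 / +0.0026 |
| 0.8 | 6 months | +0.0049 / +0.0110 | +0.0025 / +0.0049 |
| 0.9 | 3 months | +0.0008 / +0.0019 | +0.0007 / +0.0014 |

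The mean lag to a quarterly meeting is 1.5 months and the longest is 3. Six months would need late reading or reopening, which the protocol does not describe. With median OS from 18 to 48 months, the shift at 0.8 with up to 3 months known runs from +0.0003 to +0.007. If judgement is confined to the up to 10% of patients without a LAP (section 1.2), it is at most +0.0006; a study using different-from-normal throughout would have a larger share.

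For scale, SE(R) ≈ (1 − R²)/√(k − 3). The protocol does not give the number of comparisons k; 7 is borrowed from the earlier EFS work in section 9.1.3. At R = 0.8 this is 0.36/2 = 0.18, so +0.0054 is 3% of one standard error.

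A cruder second model re-reads as positive a share of the MRD-negative patients with a known event, with 5% to 30% of patients having one. At a 10% share, a true R_T of 0.80 becomes 0.80 to 0.81. Re-reading half of them would take it to about 0.82 to 0.87, a rate nothing in the documents suggests.

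**Step 3. Individual level.** The direction is not uniform. With the lag spread over 0 to 3 months, a true MRD-OS hazard ratio of 2.0 becomes 1.94 to 1.97 under the two-way rule and 2.03 to 2.05 under upgrade-only. A true ratio of 1.0 becomes 1.03 to 1.06 or 1.02 to 1.03.

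**The case against.** The strongest reply is that the primary reading is made alongside morphology, before later relapse or death, and is already in the database when the meeting takes place. Section 6.2 presents the conferences as harmonisation, so agreement may mean only that the two laboratories align their readings. Nothing describes adjudication or revision. Withholding the arm also blocks the more dangerous route, re-reading in favour of a treatment. Laboratory data pass through certified systems first, so a source value probably survives, and the choice of reading is a natural SAP item.

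Most of this stands, and it limits the point. A reader might infer that MRD values are changed in the light of outcome and that the surrogacy result is therefore circular. The documents do not support that: they show that outcome is available at the discussion, and no more. A reader might also infer that the plan has no safeguard at all. That too goes beyond the text, because two manuals and the SAP are unseen.

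The criticism of the arithmetic is also fair. The two-way rule counts a positive patient alive at three months as discordant, which is unlikely reader behaviour when median OS is two years, and it produces most of the larger shifts. Relapse is not modelled.

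What remains is that none of these replies hides outcome at the conferences or names the value analysed. The authors chose to withhold the arm explicitly, and the protocol gives no reason why aligning two laboratories' readings needs dates of death.

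**Conclusion.** The point holds as a low-severity improvement. Supplying outcome to the conferences is a stated procedure. The protocol does not mask members to outcome or say which reading enters the primary analysis.

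The size cannot be derived from the documents. Under the assumed inputs the R_T shift is negligible: up to about +0.005 at 0.8 with at most 3 months of outcome known and median OS of 24 months, against a standard error of about 0.18 with 7 assumed comparisons. A claim that the primary test would be materially inflated is not supported. The post-consolidation reading may be discussed with more outcome known, but its surrogacy analysis is exploratory.

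The main harm is a circularity objection that would be hard to answer afterwards unless a pre-linkage value had been kept and designated for analysis. Confidence is medium because the manuals and SAP may already deal with this.

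**What to change.** Section 8: do not show the conferences the outcome items, namely post-baseline date of relapse, date of death or last follow-up, and vital status. Withhold the date of allogeneic HCT when the post-induction or post-salvage reading is discussed. Keep:

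- baseline data, including the baseline date of diagnosis or relapse, which anchors the LAP reference in relapsed AML and must be kept distinct from the outcome relapse date;
- response status, which is assessed together with MRD and is needed for the different-from-normal rule (non-response is an EFS event, so this remains a limit of the secondary EFS analysis);
- the HCT date where it is needed to check the timing of the post-consolidation sample.

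Section 6.2 and the SAP: state that the primary analysis uses the laboratory value documented before the conference and before outcome linkage. Log any later change, with its reason, in the existing database and use changed values only in a sensitivity analysis. If a manual already contains these rules, a cross-reference is enough.

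Cost: a few sentences, a restricted database view for the conferences, and slightly less clinical context for those attending.

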9.1 Design aspects

Clinical development of new drugs in hematology/oncology is an increasingly challenging endeavor. With the number of new compounds that can potentially be tested in the clinic, and the need to reach conclusions about the safety and efficacy of new treatments as quickly as possible, the search for early clinical endpoints and biomarkers that can be used as surrogate endpoints for long-term clinical endpoints has emerged as a new discipline in its own right [35]. Prentice's definition of a surrogate endpoint was that of a response variable for which the test of the null hypothesis of no relationship to the treatment groups under comparison was also a valid test of the corresponding null hypothesis based on the true endpoint [36]. Subsequently, Freedman et al. and Buyse and Molenberghs emphasized estimation and prediction rather than hypothesis testing in the process of endpoint validation [37][38]. The measures proposed using data from a single trial, such as the proportion of treatment effect explained, have however been shown to be insufficient to establish surrogacy [39]. The focus therefore shifted to methods based on a meta-analytic approach using data from several randomized trials [40][41]. When data from several trials are available, a surrogate endpoint can be assessed both at the individual level and at the trial level for its ability to predict the effect of treatment on the true endpoint. Using the trial level association between the effects of treatment on the surrogate and on the true endpoint, a calculation of the surrogate threshold effect (STE), which is the minimum effect required on the surrogate to predict a significant effect on the true endpoint in a future trial can be performed [42]. Hence, if a surrogate was accepted as valid (qualified), a future trial could be designed to show that the treatment effect on the surrogate exceeds the surrogate threshold effect, rather than to show a treatment effect on the true endpoint. Therefore, our aim is to benefit from our established trial infrastructure with randomized interventional clinical trials running in parallel and to evaluate MPFC as a general approach to measure MRD for surrogacy in respect to survival endpoints.

9.1.1 Experimental assessment:

MRD assessed by flow-cytometry as described previously [5][6][7][8][21][22][23][24][25][26][27] is assessed in patients after induction (newly diagnosed AML) or salvage chemotherapy (relapsed/refractory AML) and after completion of consolidation therapy (newly diagnosed AML and relapse/refractory AML) in the two laboratories at the University Hospital Heidelberg and the University Hospital Dresden. MRD assessed by MPFC will be evaluated first at the same time as the remission status based on morphology after induction/salvage therapy. This MRD assessment by MPFC after induction/salvage therapy is used to test the primary hypothesis. A second MRD assessment by MPFC will be performed after completion of consolidation therapy including high-dose chemotherapy and alloHCT. MRD positive values are documented as discrete numbers up to 100%.

[figure not shown]
9.1.2 Standard assessment:

Overall survival (OS) is defined as time from entry into the study until death from any cause. Event-free survival (EFS) is measured from entry into the study until one of the following events, whichever comes first, i) no response to induction therapy, ii) relapse, iii) death from any cause. For assessment of response to induction therapy and relapse, morphological evaluation of peripheral blood and bone marrow smears is the standard assessment. Relapse-free survival (RFS) is measured in patients who achieve a first CR. RFS is measured from achievement of first CR until one of the following events, whichever comes first i) relapse, ii) death from any cause. For assessment of relapse morphological evaluation of peripheral blood and bone marrow smears is the standard assessment. OS, EFS, and RFS are censored at the date of last follow up in case of no event. The survival endpoints OS, EFS, and RFS defined according to the ELN recommendations [1] are accepted standards. Within the proposed study the primary survival endpoint is OS, EFS and RFS are included as secondary survival endpoints.

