9.1.4 Statistical Analysis

With respect to Prentice's original proposal [36] current consensus is that for surrogate validation a correlation-based approach can be applied, with estimation of correlation measures on a trial level and an individual patient level [51][52][53]. We will apply the correlation approach according to Buyse et al. [40] to investigate the validity of MRD assessed by MPFC as surrogate endpoint for the long-term time to event endpoints OS (primary endpoint), RFS, and EFS (secondary endpoints). Two levels of surrogacy will be considered. On an individual patient level we will assess how well the surrogate predicts the survival endpoint. This is done by evaluating the prognostic value of MRD assessed by MPFC for the survival endpoint after adjustment for treatment. We will use the R^2 measure of Schemper and Henderson as well as Brier Score to assess the predictive accuracy of MRD assessed by MPFC [54]. Within the trial-level evaluation an individual patient data (IPD) meta-analytical approach will be used to test if the treatment effect on MRD assessed by MPFC allows reliable prediction of the treatment effect on the survival endpoints. We consider logistic regression for the surrogate endpoint MRD assessed by MPFC to achieve odds ratios (OR) and the proportional hazards model of Cox for the survival endpoints resulting in per trial hazard ratios (HR) and an error-in-variables linear

regression model of the log transformed HRs on the log transformed ORs. The trial-level coefficient of determination R_T^2 is then used to quantify the strength of association between the treatment effects on MRD assessed by MPFC and on the survival endpoints at the trial level.

In addition the surrogate threshold effect (STE) [42] will be estimated as the minimum effect of MRD assessed by MPFC that predicts a statistically significant effect on EFS, RFS and OS.

In addition, exploratory analyses will be performed on

- MRD assessed by MPFC after consolidation as a surrogate for OS, EFS and RFS
- Correlation of MRD assessed by MPFC after induction therapy and after consolidation therapy with respect to applied postremission treatment

A detailed statistical analysis plan (SAP) will be finalized before database closure.

10 Quality assurance and monitoring

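### Individual-level prediction of EFS by MRD counts non-response judged at the same assessment as the MRD reading, with no landmark (minor, secondary analysis only)

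*Combined protocol and SAP*

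**What the plan says.** Section 9.1.2 starts the EFS clock at study entry and runs it "until one of the following events, whichever comes first, i) no response to induction therapy", relapse or death. Response is judged by morphology of blood and marrow smears.

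Section 9.1.1 fixes the timing of the candidate surrogate: "MRD assessed by MPFC will be evaluated first at the same time as the remission status based on morphology after induction/salvage therapy". It adds that "MRD positive values are documented as discrete numbers up to 100" percent, so there is no upper limit that would exclude overt disease.

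Section 9.1.4 evaluates MRD "as surrogate endpoint for the long-term time to event endpoints OS (primary endpoint), RFS, and EFS (secondary endpoints"). Its patient-level part reads "On an individual patient level we will assess how well the surrogate predicts the survival endpoint". This is done through prognostic value adjusted for treatment, the Schemper-Henderson R² "as well as Brier Score to assess the predictive accuracy of MRD assessed by MPFC". No landmark, delayed entry, time-dependent MRD covariate or restriction to event-free patients is given for EFS.

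On who has an MRD value, section 7.1 says "MRD assessed by MPFC is documented for patients who at least have one MPFC result at diagnosis/relapse" and one result after induction or salvage. That sentence sets no condition on response. Only the route for patients without an evaluable leukemia-associated phenotype (LAP) refers to responders. Section 3.1 intends MRD in all evaluable patients.

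**The concern.** For a patient who does not respond, the predictor and the event are established at one assessment. A non-responder with overt marrow disease is likely to be MRD-positive, and the same visit supplies the EFS event. A model of EFS from entry then credits MRD with anticipating something that had already happened when MRD was read.

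What is at stake is the interpretation of one secondary set of figures. A patient-level R², Brier score or hazard ratio for EFS could be read as evidence that MRD foretells later relapse or death when part of it repeats the morphological finding. In a study whose purpose is surrogate validation, such a figure is easily cited as support. OS has death as its only event and RFS starts at CR, so neither contains non-response as an event.

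**Working it through.** The plan gives no figure for this analysis, so there is nothing to reproduce. The check has three steps.

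**1. How many EFS events may already be present at the MRD visit**

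Section 1.1 gives CR rates of 65-75% in younger and about 40-60% in older patients, a range of 40-75%. Let d be the proportion dying early without a sample (assumed 0 or 10%). The non-responder share of sampled patients is f = (1 - CR - d)/(1 - d):

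- d = 0: CR 40, 60, 75% gives f = 60, 40, 25%.
- d = 0.10: f = 0.50/0.90 = 55.6%, 0.30/0.90 = 33.3%, 0.15/0.90 = 16.7%.

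Each patient has at most one EFS event. If q is the probability that a responder has an event during follow-up, the share of EFS events present at the visit is f/(f + (1 - f)q). This is at least f, hence at least 17-60%. At the top end (f = 0.60, median EFS after CR 18 months, about 34.75 months of follow-up after the visit), q = 1 - 0.5^(34.75/18) = 0.738 and the share is 0.60/(0.60 + 0.40 × 0.738) = 0.67. The simulation to 36 months gives 17-67%.

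**2. The mechanism by hand**

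Take f = 0.25 and half of responders MRD-positive, with MRD carrying no information about their later course.

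- All non-responders positive: 0.25/(0.25 + 0.375) = 40% of the MRD-positive group has failed at the visit, against 0% of the MRD-negative group.
- 80% positive: 0.20/(0.20 + 0.375) = 35%, against 0.05/(0.05 + 0.375) = 12%.

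The curves separate at the visit and nothing prognostic has occurred.

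The contrast at the visit can also be weaker than a true effect. With f = 0.60, 70% of responders positive and 80% of non-responders positive, the failed proportions are 0.48/0.76 = 63% and 0.12/0.24 = 50%, a ratio of 1.26. Mixed with a true responder hazard ratio of 2, this pulls the estimate down.

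**3. Simulation**

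There are 36 scenarios of 200,000 patients each: the six values of f above; 30, 50 or 70% of responders MRD-negative; median EFS after CR of 9 or 18 months (exponential). The MRD visit is at 1-1.5 months, non-response is an event at that visit, and follow-up is 36 months. MRD is positive/negative. Brier explained variation is 1 minus the Brier ratio at 12 months.

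| Non-responders MRD-positive | HR from entry, true responder HR 1 | HR from entry, true responder HR 2 | Brier explained variation, true HR 1 |
|---|---|---|---|
| 100% | 1.27-4.04 | 2.33-5.46 | 0.007-0.313 |
| 95% | 1.22-3.46 | 2.21-4.60 | 0.005-0.256 |
| 80% | 1.08-2.41 | 1.65-3.10 | 0.001-0.135 |
| Landmark at the visit | 0.99-1.02 | 1.97-2.04 | at most 0.0001 |

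- At 80% positivity and a true hazard ratio of 2, the estimate from entry fell below 2 in 12 of the 36 scenarios.
- With only 10% non-responders (response defined more widely than CR) and true HR 1, the hazard ratio from entry is 1.16-1.47, 1.12-1.43 and 1.05-1.32 at 100, 95 and 80% positivity.
- With one common visit time and all non-responders positive, handling of ties matters: 1.25-2.77 (Breslow) or 1.28-4.00 (Efron).
- A separate simulation (1000 patients, 40% of responders positive, median 15 months after assessment, 10-60% non-response, 80-100% of non-responders positive) gave 1.2-3.2 from entry for an uninformative marker, against 0.95-1.02 from a landmark.

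Not simulated: the Schemper-Henderson R², MRD as a continuous value, and the treatment adjustment.

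**The case against.** The strongest objection is that the analysis set is not stated. Section 7.1 is silent on response for the LAP route, and section 3.1 does not define evaluable. The rationale places MRD in remission: the Summary speaks of first CR, and section 1.1 of patients once CR is reached. Values up to 100% are weak evidence, since section 1.2 uses the same scale for any positive MRD. This stands: inclusion of non-responders is the natural reading, but an inference.

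Second, the patient-level sentences in section 9.1.4 speak of a single survival endpoint. The sentence introducing the approach lists OS, RFS and EFS, so EFS is very probably covered, though no EFS model is spelled out.

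Third, RFS is already planned and starts at CR, so for newly diagnosed patients most of the clean estimate will exist. This stands, and it keeps the point minor. It does not label the EFS figure, which would still be reported with its own R² and Brier score.

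Fourth, EFS follows a definition the protocol calls an accepted standard, and the SAP is still to be finalised. Both are true. The definition is not at fault; using it to score a marker read when the event is declared is. A pending SAP is the place to settle this.

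A reader might infer that the primary hypothesis is compromised. The documents do not support that: section 9.1.3 tests the trial-level correlation of treatment effects on MRD and OS, and EFS plays no part. Nor do they support saying that non-responders are certainly in the data, or that the distortion is always upward.

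**Conclusion.** The point holds as a minor one on a secondary analysis. As written, the plan lets an event judged at the MRD assessment count as something MRD predicted, provided non-responders enter the patient-level EFS analysis.

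The size cannot be fixed from the documents. For a marker with no value among responders, the illustration gives a hazard ratio from entry of about 1.1-4.0 and up to about 31% Brier explained variation at 12 months; a landmark returns about 1 and essentially zero. With 10% non-responders the hazard ratio is about 1.05-1.5. These figures rest on general CR rates rather than those of the participating trials, and on assumed early deaths, event times and MRD positivity. Positivity in non-responders is undocumented; the 0.1% cut point in section 1.2 makes a high rate plausible, no more. The documents also give no CR rate after salvage and no number of relapsed patients. If only CR patients are analysed, the overlap is nil.

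**What to change.** In the SAP:

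- State whether non-responders belong to the patient-level MRD-EFS analysis set.
- Run that analysis (prognostic effect, R², Brier score) from a landmark at the post-induction/salvage MRD assessment, in patients alive and event-free at that point. Report it beside the planned RFS analysis, with which it nearly coincides in newly diagnosed patients.
- Label any EFS-from-entry figure as including non-response read at the same visit as MRD.
- Leave the trial-level EFS analysis by randomised arm unchanged, with the same caveat on its R_T and on the surrogate threshold effect for EFS.

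No new data are needed: the section 8 export already contains "response to induction/salvage treatment, date of assessment, date of response", together with relapse and death dates.

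The cost is a smaller analysis set and figures that will usually look less favourable. Of the 1000 patients assumed in section 9.1.3, about 1000 × (1 - 0.60) = 400 to 1000 × (1 - 0.167) = 830 remain. Simulated with a hazard ratio of 2, median 12 months, 36 months of follow-up and no dropout, the standard error of the log hazard ratio is at most 0.118 with 400 patients and 0.083 with 830. The 95% intervals are then 2 × exp(±1.96 × 0.118) = 1.59-2.52 and 2 × exp(±1.96 × 0.083) = 1.70-2.35, so precision remains adequate.
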